6.4.3.8 Follow-up of unresolved adverse events

Any AEs that are ongoing at the end of the study (Visit 11) or at discontinuation, will be followed up until resolution by the investigator or until the investigator decides that no further follow-up is necessary, but without further recording in the eCRF. AstraZeneca retains the right to request additional information for any patient with ongoing AEs/SAEs at the end of the study, if judged necessary. The requirement to follow-up is not intended to delay database lock or production of the clinical report. Both these activities should proceed as planned with ongoing AEs if necessary.

Any follow-up of ongoing SAEs after database lock will be reported to AstraZeneca, who will notify the appropriate Bristol-Myers Squibb Pharmacovigilance contact.

6.4.3.9 Adverse event reported after the end of treatment

Only unsolicited SAEs will be collected for a period of up to 30 days after the last dose of investigational products. All SAEs and associated concomitant medication will be recorded and reported to AstraZeneca who will notify Bristol-Myers Squibb Pharmacovigilance (see Section 13.1).

6.4.3.10 Reporting of hypoglycaemic events

Hypoglycaemic events (see Section 6.4.9) should be reported in a separate "Hypoglycaemic Adverse Event module" section in the eCRF. Hypoglycaemic events are considered non-AE in this protocol by the nature of the primary endpoint selected for the present study.

Hypoglycaemic events should not be recorded in the regular AE section, except if the hypoglycaemic event fulfils the definition for a SAE, when it should be reported in the SAE section in the eCRF.

6.4.4 Reporting of serious adverse events

All SAEs have to be reported, whether or not considered causally related to the investigational products, or to the study procedure(s). All SAEs will be recorded in the eCRF.

If any SAE occurs in the course of the study, then investigators or other site personnel inform appropriate AstraZeneca representatives within one day, ie, immediately but **no later than the end of the next business day** of when he or she becomes aware of it.

The designated AstraZeneca representative works with the investigator to ensure that all relevant information is provided to Bristol-Myers Squibb Global Pharmacovigilance & Epidemiology **within one calendar day** of initial receipt for all SAEs. The AstraZeneca representative will notify the appropriate Bristol-Myers Squibb Pharmacovigilance contact to ensure regulatory compliance.

For fatal or life-threatening AEs where important or relevant information is missing, active follow-up is undertaken immediately. Investigators or other site personnel inform AstraZeneca representatives of any follow-up information on a previously reported SAE within one calendar day, ie, immediately but **no later than the end of the next business day** of when he or she becomes aware of it.

The reference document for definition of expectedness/listedness is the Investigator Brochure for the investigational product, and the EU Summary of Product Characteristics (SPC) for the active comparator product (including any AstraZeneca comparator).

6.4.4.1 Serious adverse event handling using Web Based Data Capture Rave

Serious Adverse Event (SAE) information will be entered and submitted into the Web Based Data Capture (WBDC) system Rave (Medidata) on the relevant eCRF modules. An automated e-mail alert will be sent to the designated AstraZeneca representative who will work with the investigator to ensure that all the necessary information is available in the system within the required time frames. AstraZeneca representative will send a completed SAE report to the appropriate Bristol-Myers Squibb Pharmacovigilance representative via fax or e-mail.

If the WBDC system is not available, then the investigator or other study centre personnel reports a SAE to the appropriate AstraZeneca representative by telephone. The AstraZeneca representative will advise the investigator/study centre personnel how to proceed.

A paper back-up SAE report should be sent to AstraZeneca representative, who will notify Bristol-Myers Squibb, recognising that the same reporting time frames still apply. The investigator is responsible for completing the eCRF as soon as the system becomes available again.

6.4.5 Laboratory safety assessment

Blood and urine samples for determination of clinical chemistry, haematology and urinalysis tests will be taken at the times indicated in Table 3. The date and time of sampling will be recorded on the laboratory requisition form. The samples will be processed by the Central Laboratory and results will be reported back to the study centre within 72 hours.

The complete list of safety laboratory variables is displayed in Table 3.

Visit number	S	1	2	3	4	5	6	7	8	9	10	11
Study Week	-6	-4	-2	0	3	6	9	12	24	32	40	52
Haematology												
Haemoglobin		Х							Х			Х
Haematocrit		Х							Х			Х
Red blood cell count		Х							Х			Х
White blood cell count and differential		Х							Х			Х
Platelet count		Х							Х			Х
Clinical chemistry												
Aspartate Aminotransferase (AST)		Х							Х			Х
Alanine Aminotransferase (ALT)		Х							Х			Х
Alkaline Phosphatase		Х							Х			Х
Creatine Kinase (CK)		Х							Х			Х
Total Bilirubin (TB)		Х							Х			Х

Table 3Safety laboratory variables

Visit number	S	1	2	3	4	5	6	7	8	9	10	11
Study Week	-6	-4	-2	0	3	6	9	12	24	32	40	52
Total Protein		Х							Х			Х
Albumin		Х							Х			Х
Blood Urea Nitrogen (BUN)		Х							Х			Х
Electrolytes:		Х							Х			Х
- Sodium - Potassium - Chloride												
TSH ^a		Х										
Serum Creatinine (SCr) ^b		Х							Х			Х
Urinalyses												
рН		Х							Х			Х
Protein ^c		Х							Х			Х
Glucose		Х							Х			Х
Leukocyte esterase ^c		Х							Х			Х
Blood by dipstick ^c		Х							Х			Х
Albumin:creatinine ratio		Х							Х			Х

Table 3Safety laboratory variables

a. If abnormal, reflex to free T4

b. Creatinine clearance (CrCl) will be estimated by the method of MDRD (Levey et al 1999)

c. Microscopy if dipstick positive for protein, leukocyte esterase or blood

All samples should be taken by adequately trained study centre personnel, and performed and handled in accordance with given instructions in the Laboratory Manual. Up to date reference ranges will be provided during the study and laboratory results will be compared to the laboratory standard normal ranges and flagged if they are outside the normal range. The investigator should make an assessment of the available results with regard to clinically significant abnormalities. The laboratory reports should be signed and retained at the study centre as source data for laboratory variables.

For information on how AEs based on laboratory tests should be recorded and reported, see Section 6.4.3.

For blood volume, see Section 7.1

6.4.6 Physical examination

The physical examination includes the following: General appearance, lymph nodes, thyroid, cardiovascular, lungs, abdomen, reflexes, musculoskeletal and extremities. Baseline data is collected at Visit 1, and findings are entered into the eCRF. New findings at the physical examination at Visit 11 are recorded as change from baseline.

The brief physical examination includes: General appearance, cardiovascular, lungs, abdomen and extremities to verify the findings from the physical examination at baseline and will be performed at Visit 3, and the eCRF will be completed.

For information on how AEs based on examinations and tests should be recorded and reported, see Section 6.4.3.

6.4.7 ECG

A 12-lead ECG will be taken (supine position, standard ECG with a paper speed of 50 mm/second covering at least 6 sequential beats) after the patient has been lying down resting for at least 5 minutes. The ECG will be evaluated by the investigator and entered as 'Normal' or 'Abnormal' in the eCRF.

ECG will be assessed at Visit 1 and Visit 11.

For information on how AEs based on examinations and tests should be recorded and reported, see Section 6.4.3.

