2.3 Safety objective

- Safety and tolerability will be evaluated by assessment of AEs, laboratory values, electrocardiogram (ECG), pulse rate, blood pressure, body weight and physical examination

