6.4.3.6 Adverse events based on examinations and tests

The results from protocol mandated laboratory tests and vital signs will be summarised in the clinical study report (CSR). Deterioration as compared to baseline in protocol-mandated laboratory values, vital signs and other safety variables should therefore only be reported as AEs if they fulfil any of the SAE criteria or are the reason for discontinuation of treatment with the investigational products or meet the requirements for regulatory reporting, as described in Section 6.4.2.

If deterioration in a laboratory value/vital sign is associated with clinical signs and symptoms, the sign or symptom will be reported as an AE and the associated laboratory result/vital sign will be considered as additional information. Wherever possible, the reporting investigator uses the clinical, rather than the laboratory term (eg, anaemia versus low haemoglobin value). In the absence of clinical signs or symptoms, clinically relevant deteriorations in non-mandated parameters should be reported as AE(s).

Deterioration of a laboratory value, which is unequivocally due to disease progression, should not be reported as an AE/SAE.

Any new or aggravated clinically relevant abnormal medical finding at a physical examination, as compared with the baseline assessment, will be reported as an AE.

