11.2.4 Baseline and change from baseline

Baseline is defined to be Visit 1 for safety variables. Change from baseline will be calculated as absolute difference between the value measured at or derived for a specific time point after baseline minus baseline value.

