12.4.1 Independent Adjudication Committee

An Independent Adjudication Committee, blinded to the treatment of the patient, will classify cardiovascular AEs, such as, but not limited to, myocardial infarction and stroke reported in the study. A separate Adjudication Manual will define and describe the procedure for the handling, reporting and classification of these events.

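### The Normal/Abnormal ECG entry cannot register worsening in a patient already abnormal at Visit 1, and Section 6.4.3.6 keeps the asymptomatic, non-serious part of that worsening off the AE list

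*Protocol*

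**What the plan says.** Section 2.3 of the protocol makes ECG part of the safety objective: "Safety and tolerability will be evaluated by assessment of AEs, laboratory values, electrocardiogram (ECG), pulse rate, blood pressure, body weight and physical examination".

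Section 6.4.7 fixes when it is done and what is stored: "ECG will be assessed at Visit 1 and Visit 11", and "The ECG will be evaluated by the investigator and entered as 'Normal' or 'Abnormal' in the eCRF". For AE recording it refers the reader to Section 6.4.3. Section 11.2.4 sets the reference point, "Baseline is defined to be Visit 1 for safety variables", and defines change as an absolute difference.

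Section 6.4.3.6 first says that mandated laboratory tests and vital signs will be summarised in the clinical study report. From this it concludes that deterioration in laboratory values, "vital signs and other safety variables should therefore only be reported as AEs if they fulfil any of the SAE criteria", cause discontinuation of the investigational product, or meet the regulatory reporting requirements of Section 6.4.2.

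Physical examination is treated differently. Section 6.4.6 says "New findings at the physical examination at Visit 11 are recorded as change from baseline", and Section 6.4.3.6 makes any new or aggravated clinically relevant examination finding an AE.

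Section 12.4.1 sets up a blinded committee that "will classify cardiovascular AEs, such as, but not limited to, myocardial infarction and stroke reported in the study".

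**The concern.** A two-level code separates better from worse only across the boundary between its levels. Exclusion criterion 1 in Section 4.2 removes an ECG abnormality only if it is clinically significant and would compromise safety or successful participation. Patients aged 65 and over with other abnormal tracings can therefore be randomised. For them, Abnormal at Visit 11 means either the same tracing or a new problem, and the field does not say which.

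The AE list would be the natural place to catch the difference, but Section 6.4.3.6 narrows that route. What escapes both records cannot be recovered at analysis, because the data were never collected. A statistical analysis plan cannot repair that.

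At stake is the ECG part of the safety comparison. Section 1.2 states that saxagliptin has a safety and tolerability profile comparable to glimepiride, and Section 1.3 says that very little data exist in patients aged 75 and over. The primary and key secondary endpoints are not touched.

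**Working it through.** The protocol gives no figure on this point, so there is none to reproduce. The check is a reading of the rules against each other, with one illustrative count.

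**Step 1: what the ECG field can show.**

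| Visit 1 | Visit 11 | What the field registers |
|---|---|---|
| Normal | Normal | no change |
| Normal | Abnormal | worsening |
| Abnormal | Normal | improvement |
| Abnormal | Abnormal | stable or worse, not distinguishable |

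Only one cell registers worsening, and it needs a normal tracing at Visit 1. Among patients abnormal at Visit 1, the field registers worsening in none. The absolute difference of Section 11.2.4 does not help, because a two-level entry has no numerical difference.

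**Step 2: which AE routes remain for the Visit 11 ECG.** Section 2.3 lists ECG among the safety assessments, so the natural reading is that it falls under the other safety variables of Section 6.4.3.6.

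- *Serious.* Open. Section 6.4.2 includes important medical events.
- *Reason for discontinuation.* Open in the text, and it covers non-serious events. For the scheduled post-baseline ECG it has little practical reach. Visit 11 is the end of treatment or, for early leavers, the visit done because they are stopping (Table 1, footnote b; Section 5.8.1).
- *Regulatory reporting.* Section 6.4.2 lists pancreatitis, opportunistic infections and combined liver abnormalities. No ECG finding is among them.
- *Symptoms.* Open. Section 6.4.3.5 collects any health problem reported by the patient or observed.
- *Physical examination at Visit 11.* Open, if the change also produces an examination finding.

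What none of these catches is a change that is asymptomatic, not serious, not the reason for stopping and without an examination finding, but still clinically relevant.

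**Step 3: what lies downstream of the AE list.** The adjudication committee (Section 12.4.1) classifies AEs. The review for other significant AEs (Section 11.2.2) also starts from the AE list. Neither sees the residual group.

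**Step 4: whether the protocol's own rules fit together for ECG.**

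- The reason given in Section 6.4.3.6 is that results are summarised elsewhere. It names laboratory tests and vital signs; the conclusion then extends to other safety variables, for which no such summary is named.
- Section 6.4.1 gives the electrocardiogram as an example of an investigation whose abnormal result can be an AE. Section 6.4.3.6 largely withdraws that.
- Section 6.4.3.6 makes clinically relevant deterioration in non-mandated parameters an AE even without symptoms. A test that the protocol does not require is thus reported more fully than the mandated ECG.

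**Step 5: illustrative size.** Input: 698 randomised and treated patients (Section 12.3). Assumption: a share b of them is abnormal at Visit 1, with b from 20% to 60%; the protocol gives no value.

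Patients in whom the field cannot register worsening = b × 698.

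- b = 20%: 0.20 × 698 = 139.6, about 140
- b = 60%: 0.60 × 698 = 418.8, about 419

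This counts patients in whom the field is blind to worsening. It does not count missed events.

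**The case against.** The best case against the point is that the gap is narrow and the endpoint minor. Most clinically important ECG changes would arrive as symptoms, as serious events (including important medical events) or with an examination finding, and cardiovascular AEs are then adjudicated blind. ECG is one of several descriptive safety assessments, with no hypothesis test attached. The coarse code applies to both arms under blinding, so no directional bias is shown. The eCRF itself is not at hand and may hold further ECG fields. All of this stands. It limits the weight of the point but does not close the gap in Step 2.

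A reader might infer more than the documents support:

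- *That all non-serious ECG worsening is kept off the AE list.* It is not. Discontinuation is a separate route, and symptoms are AEs in their own right.
- *That no usable ECG summary exists, or that the ECG evidence rests only on patients normal at baseline.* Section 12.2.2 summarises categorical variables by counts and proportions, so the proportion abnormal at Visit 11 can be compared between randomised arms. Patients abnormal at Visit 1 count in that proportion and can also move to Normal.
- *That a planned shift table would report worsened patients as unchanged.* The protocol specifies no such table.
- *That a number of missed cases can be given.* That needs a rate of true worsening and the share already caught by the other AE routes. The documents give neither.

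**Conclusion.** The point holds in a limited form. As Section 6.4.7 is written, the ECG entry cannot register worsening in a patient already abnormal at Visit 1. As Section 6.4.3.6 is written, the asymptomatic, non-serious but clinically relevant part of that worsening at Visit 11 is not an AE either. It is therefore recorded nowhere stated in the protocol and does not reach adjudication.

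The conclusion rests on two readings: that ECG is one of the other safety variables in Section 6.4.3.6, and that the entry described in Section 6.4.7 is the only ECG result field. The number affected is unknown, and the range of 140 to 419 patients follows entirely from the assumed 20% to 60%. The primary and key secondary analyses are unaffected. This is a cheap improvement to safety data capture and does not threaten the trial's main conclusion.

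**What to change.** In Section 6.4.7, add one Visit 11 item comparing the tracing with that of Visit 1, with three answers: no change; change, not clinically relevant; new or aggravated clinically relevant finding (specify). Tabulate it by treatment arm.

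In Section 6.4.3.6, reconcile the text with Section 6.4.1 by extending the existing physical-examination rule to ECG, so that a new or aggravated clinically relevant ECG finding is reported as an AE. It then also reaches the adjudication committee when it is cardiovascular.

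Cost: one eCRF item and a protocol amendment, which under Section 8.5 needs approval by each Ethics Committee, in a study of about 175 centres. A few more AEs will be reported, and the comparison carries some investigator subjectivity, though under blinding. No extra tracing, visit or staff is needed, because the investigator already evaluates both ECGs.

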6.4.8 Other variables

Other variables will be assessed following the Study Plan and Time Schedule outlined in Section 3.1, and results are entered into the eCRF.

Blood pressure and pulse rate

Blood pressure and pulse rate will be measured using a standardized cuff adapted to the size of the patient's arm after the patient has been sitting and resting for at least 5 minutes and before blood samples are taken.

Weight and height

The patient's weight will be recorded in kilogram (kg) on a fasting stomach with light clothing and no shoes. The patient's height will be recorded (at Visit 1) in centimetres, with no shoes.

Waist circumference

The waist should be measured (in centimetres) in the morning before breakfast in the standing position at the natural waist (smallest waist circumference). If there is no natural waist, the measurement should be made at the level of the umbilicus.

6.4.9 Hypoglycaemic events

The patient will be asked always to self-monitor plasma glucose for symptoms suggestive of hypoglycaemia and to register if a finger-stick value was obtained and the glucose value in the supplied patient diary for hypoglycaemic events (see Section 6.5.2, 6.5.1).

A hypoglycaemic event can be either

- An event with symptoms and confirmed low glucose
- An event with low glucose
- An event with symptoms when glucose not was measured

For the evaluation of hypoglycaemic events, special attention will be given to hypoglycaemia as defined in accordance with the Committee for Proprietary Medicinal Products (CPMP) guidance on clinical investigation of medicinal products in the treatment of diabetes mellitus, and slightly adapted taking into consideration recent recommendations from the ADA Workgroup on Hypoglycaemia (Diabetes Care, 2005, 28, 1245) for severe hypoglycaemias:

- Confirmed hypoglycaemic event, defined as either a symptomatic event with plasma glucose level <3.0 mmol/L (<54 mg/dL), and no need for external assistance, or an asymptomatic plasma glucose measurement <3.0 mmol/L (<54 mg/dL).
- Major (or severe) hypoglycaemic event, defined as a symptomatic event requiring external assistance due to severe impairment in consciousness or behaviour, with or without plasma glucose level <3.0 mmol/L (<54 mg/dL), and prompt recovery after glucose or glucagon administration. These events may be associated with sufficient neuroglycopenia to induce seizure or coma. Plasma glucose measurements may not be available during such an event, but neurological recovery attributable to the restoration of plasma glucose to normal is considered sufficient evidence that the event was induced by a low plasma glucose concentration.
- Mild or moderate hypoglycaemic events where plasma glucose measurement is not available will be considered suggestive of hypoglycaemia but will not be considered in the evaluation of the primary endpoint of the present study.

Plasma glucose values will be obtained from the central laboratory and when using the glucometers provided by AstraZeneca.

Data to be collected for each hypoglycaemic event:

- Date of start and stop and time of the day for start
- If symptoms are present or not and which symptoms
- If finger-stick value obtained, and the plasma glucose value

- Intervention needed for recover, maximal intensity, action taken, causality and possible contributing factors
- Action taken with investigational products

All hypoglycaemic events reported by the patient in the Patient diary for hypoglycaemic events should be recorded in the Hypoglycaemic Adverse Event Module (HYPAE), regardless of measured glucose value.

The patient's diaries will be reviewed and data regarding hypoglycaemic events transcribed into the "Hypoglycaemic Adverse Event Module" in the eCRFs at each visit. New diaries for the next period will be handed over to the patient. If a major hypoglycaemic event occurs, or more than one mild or moderate since last visit, the patient should contact the investigator. For reporting of hypoglycaemic events/symptoms suggestive of hypoglycaemic events as AEs, see Section 6.4.3.10.

6.5 **Patient reported outcomes (PRO)**

6.5.1 Patient Diary for Glucose Measurement and Glucometers

The patients will be provided with a patient diary and a glucometer at Visit 2 to check and register their plasma glucose level at home. The measured value, capillary glucose, is recalculated by the glucometer to show the plasma value. During the lead-in period (Week -2 to Week 0) and titration period (Week 0 to Week 12), the plasma glucose level should be self-monitored at least every second day and the values registered into the patient diary. During the maintenance treatment period (Week 12 to Week 52), the plasma glucose should be monitored and registered into the patient diary at least once a week. The patients should receive instructions on the use of the glucometer, according to the manufacturer's manual.

The glucometer is equipped with a memory which should be reviewed by the study centre personnel at each visit. The patient diary will be collected at each visit and kept in the Investigator Study File, and a new patient diary for the next period will be handed over to the patient.

If self-monitored FPG is above 12.2 mmol/L (220 mg/dL), the patient is highly recommended to repeat the self-monitoring of FPG within 2 days. If this second FPG is above 12.2 mmol/L (220 mg/dL), the patient should contact the study centre and, if appropriate, be scheduled for a FPG measurement at the centre (analysed by the central laboratory).

For measurements that are associated with hypoglycaemia events, see below.

